11.1.3. Efficacy Endpoints

Efficacy endpoints are as follows:

- change from baseline in eGFR (Schwartz formula)
- change from baseline in urine protein and albumin levels
- change from baseline in LVMi
- change from baseline in FPHPQ scores
- change from baseline in PedsQL scores

11.2. Sample Size Considerations

Since this is a long-term extension study that will enroll subjects from Study AT1001-020, no formal sample size calculation was performed.

11.3. Data Analysis Considerations

11.3.1. Analysis Populations

11.3.1.1. Safety Population

The safety population will include all subjects who receive at least 1 dose or partial dose of study drug. All safety and PD analyses will be performed using the safety population.

11.3.1.2. Intent-to-treat Population

The intent-to-treat population will include all enrolled subjects. All efficacy analyses will be performed using intent-to-treat population.

11.4. Statistical Methods

For the purpose of statistical analyses, baseline is generally defined as the last non missing measurement obtained on or before the administration of the first dose of study drug. For this study, the baseline value for efficacy endpoints will be obtained from the baseline visit of Study AT1001-020.

Only summary statistics will be provided for data collected from this study. No missing data imputation method is planned to handle missing data. Data will be summarized as observed.

Data will be summarized using descriptive statistics. Continuous variables will be summarized by number of subjects, mean, standard deviation, median, minimum, and maximum values. Discrete variables will be summarized by counts and percentages.

In general, data will be summarized by age group at baseline, by sex, and combined across all subjects.

A month will be defined as 30 days.

No missing data imputation method is planned to handle missing data. Data will be summarized as observed. All data will be listed.

Full details will be presented in the SAP.

11.4.1. Interim Analysis

No interim analyses are currently planned for this study.

11.4.2. Baseline Demographic and Subject Characteristics

Baseline demographics and subjects' characteristics will be presented for all subjects in the intent-to-treat and Safety Populations. Demographics will be collected from the baseline visit of Study AT1001-020. Age at entry into this study will be re-calculated based on the date of birth recorded in the Study AT1001-020. Subject characteristics will be summarized using descriptive statistics.

Subject characteristics will be updated from Study AT1001-020 and will include height, body weight, body mass index, number of years since diagnosis of Fabry disease, previous use of

enzyme replacement therapy, and previous and current use of angiotensin-converting enzyme inhibitors, renin inhibitors, and angiotensin receptor blockers.

11.4.3. Subject Disposition

A summary of subject disposition will include number of subjects enrolled, number of subjects in each analysis population, number of subjects who completed the study, and number of subjects who did not complete the study by reason for discontinuation.

Protocol deviations will be listed.

11.4.4. Safety Analyses

Continuous safety data will be summarized using descriptive statistics (number, mean, standard deviation, median, minimum, and maximum). Categorical variables will be presented by number (percentage).

11.4.4.1. Exposure

An exposure table will be presented based on subcategories as defined in the SAP.

11.4.4.2. Adverse Events

Adverse events will be coded using the Medical Dictionary for Regulatory Activities (MedDRA) and summarized by system organ class (SOC) and preferred term.

The number and percentage of subjects with AEs will be summarized by SOC and preferred term within each SOC. Additional displays will present AEs by intensity (mild, moderate, severe), relationship to study treatment (Related Events: definite, probable, and possible; Unrelated Events: unlikely and unrelated), and by outcome of events. Moreover, the number of AEs (as opposed to the number and percentage of subjects) will be presented. Listings will also be provided for SAEs and TEAEs leading to discontinuation of study treatment.

11.4.4.3. Laboratory Data

Actual values and changes from baseline for clinical laboratory test results will be summarized using descriptive statistics (number, mean, median, minimum, and maximum). Categorical variables will be presented by number (percentage). Shift tables will also be provided for clinical laboratory tests.

Potentially clinically significant (PCS) laboratory values will be summarized by laboratory parameter. The PCS criteria for laboratory values will be defined in the final SAP. The summary will indicate the number of subjects with PCS-low or PCS-high values at any time during treatment with migalastat, but will not be presented by visit. It is possible for subjects to appear in both categories (PCS-low and PCS-high) for any parameter. The incidence rates of PCS values will be presented. There will be no statistical testing.

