5.6.1.5. Visit Windows

There will be no derivation for visit windows in terms of summary assessments. Nominal visits will be used for by-visit tables. For data with repeated observations at a given visit (eg, laboratory assessments), the earliest of the available non-missing values at a visit should be used in summary tables. Other observations will be considered as unscheduled visits.

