9.3. Laboratory Evaluations

Clinical laboratory test values (hematology, serum chemistry, and urinalysis) and changes from baseline will be summarized by each visit and subgroup, ie, sex (male, female), ERT status (ERT naïve, ERT experienced), and overall if feasible for the enrolled population. By-visit summary will also include the last post-baseline values.

In addition, the following clinical summaries will be presented:

- Tables summarizing the frequencies and percentages of potential clinically significant (PCS; see Table 2) abnormalities at any time. The summary will indicate the number of subjects with PCS-low or PCS-high values at any time during treatment with migalastat but will not be presented by visit. PCS abnormalities will be determined both by investigator assessment and derivation from lab alert ranges provided by Amicus. PCS abnormalities that occur at unscheduled visits will be included.
- Tables displaying shifts from baseline to each assessment time-point, including the last postbaseline assessment, in laboratory test values from normal to high or low using normal range including eGFR, urine protein, and albumin.

Unscheduled visits will be included in PCS summaries and when determining the worst post-baseline assessment.

By-subject safety laboratory listings will be generated incorporating information and assessment results obtained from the designated laboratory which provided normal range and reported out of range flags. All laboratory results in Système International (SI) units will be presented in data listings. Tests will be listed in alphabetical order within their respective panels (hematology, serum chemistry, and urinalysis). Abnormal values will be flagged.

Chemistry		Hematology	
Alkaline Phosphatase	\geq 3 x Upper Limit Normal	II	$\leq 11.5 \text{ g/dL} \text{ (male)}$
AST	\geq 3 x Upper Limit Normal	Hemoglobin	\leq 9.5 g/dL (female)
ALT	\geq 3 x Upper Limit Normal	Hematocrit	$\leq 37\%$ (male)
BUN	\geq 30 mg/dL	петаюсти	$\leq 32\%$ (female)
Creatinine	$\geq 2.0 \text{ mg/dL}$	RBC count (absolute)	$<3.8 \ 10^{6}/uL \text{ or} > 5.5 \ 10^{6}/uL$
СРК	CPK $\geq 2 x$ Upper Limit Normal		$<4.5 \ 10^{3}/\text{uL} \text{ or } >13.5 \ 10^{3}/\text{uL}$
Gamma glutamyl transferase	$\geq 2 \text{ x Upper Limit Normal}$	Neutrophils	≤ 15%
Lactate dehydrogenase	\geq 300 U/L	Eosinophils	>0.7 10 ³ /uL
Glucose	\geq 100 mg/dL (fasting)	Platelet count	$\leq 75 \ 10^3/uL \text{ or } \geq 750 \ 10^3/uL$

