9.5. Electrocardiogram Results

A summary table of observed and change from baseline values in ECG results will be provided at each scheduled visit for the enrolled population. A summary table displaying shifts in interpretation from baseline to each assessment time-point, including the last post-baseline assessment, will be provided by sex (male, female), ERT status (ERT naïve, ERT experienced), and overall if feasible. By-visit summary will also include the last post-baseline values.

A by-subject listing will be provided, including each ECG parameter: heart rate (beats per minute [bpm]), PR interval [msec], QRS interval [msec], QT interval mean [msec], QTc (QTcF or QTcB) [msec] and interpretation. QTc=corrected QT interval, QTcF = corrected QT interval with Fridericia's formula, and QTcB = corrected QT interval with Bazett's formula.

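### Laboratory and ECG shift tables have no baseline-to-worst column, so milder laboratory shifts and unreported ECG changes found at unscheduled visits can end up in listings only

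*Protocol*

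**What the plan says.** Protocol 11.4.4.3 states: "Shift tables will also be provided for clinical laboratory tests". It sets no time points and no rule for unscheduled visits. Protocol 11.4.4.6 repeats the commitment for ECG results. It also promises counts of subjects with PCS-low and PCS-high ECG values over the whole study, using criteria that the SAP is to supply.

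The SAP turns this into tables as follows.

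- **Laboratory shifts (SAP 9.3):** "Tables displaying shifts from baseline to each assessment time-point, including the last postbaseline assessment".
- **ECG shifts (SAP 9.5):** "A summary table displaying shifts in interpretation from baseline to each assessment time-point, including the last post-baseline assessment".
- **Visit rule (SAP 5.6.1.5):** "Nominal visits will be used for by-visit tables". Where a visit has several values, the earliest non-missing one is used, and "Other observations will be considered as unscheduled visits". SAP 5.6.1.6 likewise keeps the first assessment.
- **Unscheduled laboratory data (SAP 9.3):** "Unscheduled visits will be included in PCS summaries and when determining the worst post-baseline assessment".

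**The concern.** The last SAP 9.3 rule above concerns a quantity that nothing displays. No table in SAP 9.3 or 9.5 shows a worst value, and the SAP does not say what worst means for a test that can be abnormal in either direction. Either a worst-value shift was intended and left out, or the sentence is a leftover. A programmer cannot tell which.

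This bears on the primary objective, which is long-term safety. Protocol 9.1.1 gives the evaluation of adverse events and the repeating of laboratory tests as reasons for unscheduled visits. Values from those visits are therefore not a random sample of the safety data. If they are kept out of the shift columns and no worst-value column exists, a transient change that has resolved by the next scheduled visit leaves those columns unchanged.

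**Working it through.** No figure in the plan needs reproducing. The check traces where a value from an unscheduled visit can enter each planned output.

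**Laboratory values**

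| Unscheduled value | By-visit shift | Last-value shift | PCS summary | Adverse event tables | Listing |
|---|---|---|---|---|---|
| Meets a limit in SAP Table 2 | No | Only if last, and if unscheduled values qualify | Yes | If reported | Yes |
| Short of the limit, investigator judges it significant | No | As above | Yes, through investigator assessment | Yes (protocol 9.2.2.2.1) | Yes |
| Outside normal, short of the limit, not judged significant | No | As above | No | No | Yes |

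The By-visit column is an inference from the nominal-visit rule in SAP 5.6.1.5; SAP 9.3 itself does not say that shifts are confined to scheduled visits.

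The third row is the gap. As an illustration with assumed values, take a subject whose ALT is normal at baseline, Month 6 and Month 12, and is 2 x ULN at an unscheduled visit in between. The investigator does not call it clinically significant.

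- Shift to Month 6: normal to normal.
- Shift to Month 12: normal to normal.
- Shift to last value, if Month 12 is the last: normal to normal.
- PCS by limit: the SAP Table 2 limit for ALT is 3 x ULN or more. Since 2 < 3, it is not flagged.
- PCS by investigator, and adverse event tables: no entry.
- Baseline-to-worst-high shift, if it existed: normal to high.

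The same route is open to any ALT or AST above 1 x ULN and below 3 x ULN.

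Some tests have no numeric limit and depend on the investigator route alone. Protocol Table 4 set against SAP Table 2 gives:

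- Chemistry: 20 analytes, 17 with a limit, so 20 - 17 = 3 without (albumin, total bilirubin, bicarbonate).
- Hematology: 10 analytes, 7 with a limit, so 10 - 7 = 3 without (basophils, lymphocytes, monocytes).
- Together: 6 of 30.

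This count is approximate. One row label in SAP Table 2 is lost in the available text and has been read as WBC.

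**ECG findings**

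- By-visit shift: no, by the same inference from SAP 5.6.1.5.
- Last-value shift: only if the ECG is the last one and unscheduled values qualify. SAP 9.5 does not say.
- PCS summary: protocol 11.4.4.6 promises one, but SAP 9.5 contains neither criteria nor table.
- Adverse event tables: yes, if the finding is new, clinically significant and meets the adverse event definition (protocol 9.2.2.6).
- Listing: yes.

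SAP section 12 declares one change, the merging of the analysis populations, and says there are no others. It measures itself against protocol Amendment 1, although the SAP introduction names Amendment 2 as its basis. Either way, dropping the ECG PCS summary found in the current protocol is not declared.

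**The case against.** The strongest reply is that the important findings are already summarized. SAP 9.3 says twice that unscheduled visits count in the laboratory PCS summary, which covers the whole treatment period. It sets PCS by investigator assessment as well as by alert range, so a flagged ALT of 2 x ULN, or a bilirubin with no numeric limit, can still be counted. Clinically significant laboratory results must be recorded as adverse events, and new significant ECG findings that meet the definition are recorded too. Those tables do not depend on visit type. All data are listed, and abnormal laboratory values are flagged. This stands. A reader might infer that abnormalities from unscheduled visits disappear from every summary; for laboratory data the documents say otherwise.

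The SAP also does not bar an unscheduled value from being the last post-baseline value. Where it excludes unscheduled visits, as for the FPHPQ in SAP 7.3.1, it says so. That stands as well, but it helps only when the abnormal value is the last one, and a resolved abnormality is not.

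A third point is that by-visit shifts are meant to show status at a visit, and feeding event-triggered values into them would distort them. That is fair, and it is why those columns should stay as they are. It does not argue against a separate worst-value column.

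Finally, the protocol sentence on laboratory shifts is not itself at fault. The omissions are in SAP 9.3, 9.5 and section 12.

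**Conclusion.** The concern holds in a limited form. No baseline-to-worst shift is specified for laboratory tests or ECGs, and the one reference to a worst value feeds no named table. Two kinds of finding can therefore be confined to listings when they come from an unscheduled visit and are not the last value:

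- laboratory values outside normal that are short of PCS and not judged significant;
- ECG changes not reported as adverse events.

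The ECG part is the stronger one, because the protocol's any-time PCS summary would have covered quantitative ECG values at unscheduled visits and it has gone without being declared.

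The size cannot be put as a number. The documents give no rate of unscheduled laboratory tests or ECGs. A reader might try to derive one from visit spacing: an episode of d days with random onset overlaps a scheduled visit with probability d/180 under 6-monthly visits, for example 28/180 = 16% for an assumed 28 days. That measures how often sampling meets an episode, with a duration the documents do not supply. It does not measure how many collected values the tables omit, and an episode that nobody sampled would be absent from any table. Nor does SAP 3.1 support a before-and-after comparison: it gives the earlier 3-monthly visit interval but not what was sampled at those visits.

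The weight is modest, since the study is descriptive and every value is listed. The change is still worth making before database lock, because it serves the primary objective and uses data already collected.

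**What to change.** 1. In SAP 9.3, define worst post-baseline and add a shift from baseline to it that includes unscheduled and repeat values. Show worst-low and worst-high separately.
2. In SAP 9.5, add the corresponding shift to the worst ECG interpretation, on the same inclusion rule.
3. Keep the by-visit and last-value shifts unchanged.
4. State in both sections whether the last post-baseline value may come from an unscheduled visit.
5. Either restore the any-time ECG PCS summary of protocol 11.4.4.6, with its criteria, or declare its removal in SAP section 12.

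The cost is SAP wording, one extra shift column per table (two for laboratory tests, if low and high are shown side by side) and some programming, plus one ECG table if the PCS summary is restored. No new data are needed. The tables will show somewhat more abnormal shifts. A footnote should say that the worst-value column includes event-triggered measurements, so that it is not read as status at a scheduled visit.

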11.4.4.4. Vital Signs

Descriptive statistics for vital signs will be presented for systolic blood pressure, diastolic blood pressure, body temperature, HR, and RR, at each visit. Change from baseline to post baseline visit will also be presented. Data will be attributed to visits as described in the final SAP.

19 August 2021 Confidential The incidence rates of PCS vital sign changes, by parameter, will be summarized. Potentially clinically significant criteria for vital signs are defined in the SAP. The summary will indicate the number and percentage of subjects with PCS-low and PCS-high values at any time during migalastat treatment and will not be presented by visit. It is possible for subjects to appear in both categories for any parameters.

11.4.4.5. Physical Examinations

Physical examination results will be presented for each body system/category examined; the number and percent of subjects judged to be normal, abnormal, or not performed will be summarized. Similarly, the results of the physical examinations will be summarized for subjects in the Safety Population who had an examination post baseline.

Tanner Stages will be summarized using descriptive statistics.

11.4.4.6. Electrocardiograms

Actual values and changes from baseline for ECG parameters will be summarized using descriptive statistics.

Potentially clinically significant values for quantitative ECG data will be summarized by parameter. The PCS criteria for 12-lead ECGs will be defined in the SAP. The summaries will indicate the number and percentage of subjects with PCS-low and PCS-high values at any time during the study, and will not be presented by visit. It is possible for subjects to appear in both categories for any parameters.

Shift tables will also be provided for clinical laboratory tests and ECG results.

11.4.4.7. Echocardiograms

Echocardiogram parameters (other than LVMi) will be summarized using descriptive statistics.

11.4.4.8. Concomitant Medications

Concomitant medications include all prescription and non-prescription medicinal treatments (including vitamins, supplements, and vaccines) taken during the treatment period. Medications that are ongoing from the Study AT1001-020 or stopped within 2 weeks of the AT1001-020 End of Study Visit, will be recorded as concomitant medications for this study. Medications from Study AT1001-020 that were stopped over 2 weeks prior to the start of this study will not be recorded as concomitant medications starting after the last dose of study drug will not be considered as concomitant, but will be flagged as post medications on the listing. All concomitant medications will be summarized.

Concomitant medications will be coded using the World Health Organization (WHO) Drug Dictionary and summarized according to the generic terms and ATC codes (Anatomical therapeutic chemical [classification system]). Medications will be tabulated in decreasing order of the total number of subjects who took each medication. In addition, the total number of subjects to ever take any concomitant medication will be presented.

11.4.5. Pharmacodynamic Analyses

Continuous plasma lyso-Gb₃ levels will be summarized using descriptive statistics. Lyso-Gb₃ analogues and exploratory cardiac biomarkers, if analyzed, will also be summarized using descriptive statistics.

11.4.6. Efficacy Analyses

Actual values and changes from baseline (as applicable) in eGFR, urine levels of protein and albumin, LVMi, FPHPQ scores, and PedsQL scores will be summarized using descriptive statistics.

12. STUDY TREATMENTS

12.1. Description of Study Drug

Migalastat is an iminosugar that functions as a selective pharmacological chaperone. Migalastat will be supplied as a gelatin capsule (Table 5). Migalastat capsules must be swallowed whole and must not be cut, crushed, or chewed.

	Investigational Product
Product Name	Migalastat
Dosage Form	Capsule
Unit Dose	123 mg (equivalent to 150 mg migalastat HCl)
Excipients	Pregelatinized starch, magnesium stearate
Route of Administration	Oral
Physical Description	White opaque/blue opaque, hard gelatin capsules (size "2"), printed with an identifying code "SGXXX" or "A1001" and supplied in blister packs
Manufacturer	Almac Pharma Services Limited [name]

Table 5:Investigational Product (Capsule)

Abbreviation: HCl = hydrochloride

12.2. Packaging and Labeling

Migalastat HCl 150-mg oral capsules will be supplied by Amicus as hard gelatin capsules in blister packs.

Each container will be labeled in conformance with regulatory requirements and where applicable, local laws. All labels will be printed with the following information at a minimum: study identifier, identity of drug and dosage, sponsor name and contact details (and/or details of a local designee contact), dosing instructions, storage information, and other applicable local law statements.

12.3. Study Drug Accountability

In accordance with local regulatory requirements, the investigator or designee must document the amount of investigational product dispensed and/or administered to study subjects, the amount returned by study subjects, and the amount received from and returned to Amicus (or designee). Product accountability records must be maintained throughout the study.

Subjects will be instructed to return all unused, partially used, or empty study drug containers at each specified visit.

19 August 2021 Confidential The study monitor will periodically check the supplies of study drugs held at the site to verify accountability of all study drugs used and to verify that the drug accountability logs are completed and maintained in the investigator study file. When instructed by the study monitor, the investigator will return all original containers of study drugs, whether empty, or containing used or unused study drugs to Amicus or designee for destruction. Sites may not destroy study drugs on site unless Amicus has provided prior written approval.

12.3.1. Handling, Storage, Return, and Disposal of Study Drugs

Sites will be instructed to store migalastat capsules at room temperature $(15^{\circ}C \text{ to } 25^{\circ}C/59^{\circ}F \text{ to } 77^{\circ}F)$ with excursions permitted to $30^{\circ}C/86^{\circ}F$ in a secure area with temperature monitoring, free from environmental extremes, and with restricted access.

A temperature log must be maintained for the duration of the study, and the temperature of the storage room (or cabinet) in which the study drugs are stored must be recorded for each working day of the week that pharmacy staff (or designated study staff) is available. Temperature is required to be recorded using a standard Min-Max Thermometer that has calibration records available (details usually contained within the device leaflet) and is maintained according to institutions standard maintenance policy.

The study drug is to be stored only at the site listed on the US Food and Drug Administration (FDA) Form 1572. Study drug is to be dispensed only to subjects from/for whom written informed consent/assent has been obtained, have met all entry criteria, and are assigned subject numbers.

